**Statistical Analysis:**

Ratios and proportions with confidence intervals will be used to estimate the incidence and grades of infusion reactions. Proportions will also be used to report the use of additional medication during and after monoclonal antibody infusions. McNemar's test will be used to compare the incidence of infusion reaction between first and subsequent infusion.

**Data Safety Monitoring and Reporting Plan:**

The Primary Investigator or Study Coordinator will monitor the research clinical study in a manner consistent with the applicable health authority regulations and the clinical standards adopted by the investigators.

The scope of the Primary Investigator or designated Study Coordinator's responsibilities include:

- Working with each Investigator and office staff to assure that the protocol, responsibilities and record keeping requirements are understood prior to initiation of the study
- Maintaining close contact with the investigators concerning the progress of the study
- Monitoring the study progress on a regular basis, semi-annually or more frequently
- Handle data entry and/or analysis
- Report Adverse Events in a timely manner

The reporting and monitoring process will be assisted by the following tools:

- A Study Data File for each patient will be created to maintain the information for each patient enrolled in the study. It will include copy of signed/dated Informed Consents and any adverse event reports.
- All submitted clinical data will go through quality assurance review, data entry and statistical analysis.

A Data and Safety Monitor (DSM) will be designated as Team A who will meet with study coordinator and Principal investigator every 4 months or after every 20 patients enrollment and will have access to the de-identified data. The data and safety monitoring team members are not part of study team.

The role of the DSM will be to:

- Evaluate the collected data for participant safety, study conduct and progress
- Make recommendations concerning continuation, modification, or termination of the trial.

The study may be stopped for one or more of the following reasons:

- Study aims are met
- Finding of Unexpected adverse effect related or unrelated to addition of Montelukast to pre-medication protocol
- The DSM determines there are significant safety issues.

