## Hypothesis

We postulate that 10 mg of Montelukast, when given at least 1 hour prior to infusion monoclonal antibodies in addition to standard premedication, will lead to at least 50% decrease in incidence of monoclonal antibody associated Standard Infusion Reactions compared to historic data. It will also lead to shorter infusion time and decrease use of additional health care resources (ER, hospitalization and discontinuation of infusion) and hence better tolerability of infusions.

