## **Purpose of the Study**

### *Aim*

To evaluate the efficacy of 10 mg of Montelukast in reducing the incidence and severity of monoclonal antibody associated standard infusion reactions (SIRs).

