### *Primary Objective*

To report the incidence of monoclonal antibody associated SIRs when 10 mg of Montelukast is added to standard premedication.

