## **Measured Outcomes:**

### *Primary endpoint*

1. To estimate the incidence rate of SIRs during above monoclonal antibody infusions.

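### Does the undefined stopping reason about the study's aims allow the trial to stop early on a favourable infusion-reaction rate?

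*Combined protocol and SAP*

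**What the plan says.** The Data Safety Monitoring and Reporting Plan introduces its list with "The study may be stopped for one or more of the following reasons". The first item is "Study aims are met". The other two concern unexpected adverse effects and significant safety issues. No section gives the first item a threshold, a time or a decision-maker.

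The same section has an independent monitor meet the coordinator and principal investigator "every 4 months or after every 20 patients enrollment and will have access to the de-identified data". The first part of the monitor's role is "Evaluate the collected data for participant safety, study conduct and progress". The second is to recommend continuing, modifying or ending the trial.

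Four other statements bear on what the aims are:
- Aim: "To evaluate the efficacy of 10 mg of Montelukast in reducing the incidence and severity" of SIRs.
- Hypothesis: "at least 50% decrease in incidence of monoclonal antibody associated Standard Infusion Reactions compared to historic data".
- Primary Objective: "To report the incidence of monoclonal antibody associated SIRs" with montelukast added to standard premedication.
- Primary endpoint: "To estimate the incidence rate of SIRs during above monoclonal antibody infusions".

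Statistical Analysis plans proportions with confidence intervals, plus a McNemar comparison of first with later infusions. It plans no test against a historic rate and no interim efficacy analysis. Sample Size anticipates 80 enrolled patients, on grounds of resources and availability.

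**The concern.** A stopping reason that is listed apart from safety and left undefined invites the question of whether it means success. The section headed Aim is about efficacy, and the Hypothesis supplies a visible target, a halving. The design lets the team watch the running SIR rate, and SIRs are both the primary endpoint and something a safety monitor would naturally see.

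If the trial stopped when that rate happened to look good, two things would follow. The reported incidence would be too low on average, because low runs would be frozen while high runs continued. It would also rest on fewer than 80 patients. Background/Significance says the result is to generate hypotheses for a randomised Phase 3 trial, so an over-favourable and imprecise rate could carry into its planning. With no planned test against history, the harm would be to the estimate and its precision, not to a stated error rate.

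**Working it through.** **1. Which reading does the text support?**

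| Question | Completion | Early success |
|---|---|---|
| What meets the aims? | Finishing the evaluation and estimating the incidence, whatever it is | A low SIR rate |
| Primary objective and endpoint | Fit: report, estimate | Do not fit: no target value |
| Secondary objectives (extra premedication, infusion duration) | Met when the data are in | Not settled by a low SIR rate |
| Threshold | None needed | None given |
| Historic rate | Not needed | Not fixed: literature and chart review across six antibodies, no number |
| Interim efficacy analysis | Not needed | None in Study Methods or Statistical Analysis |
| Monitor's remit | Consistent: safety, conduct, progress | Efficacy not named |

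Even the Aim is to evaluate efficacy, which is achieved by evaluating it. A favourable rate would support the Hypothesis, but the stopping list does not refer to the Hypothesis.

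**2. The plan's own figure.** Sample Size has no power or precision formula to reproduce. Accrual agrees with it: 40 per year × 2 years = 80.

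**3. Size of the effect if the phrase were used as a success rule.** The rule has to be invented.

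Inputs from the documents: N = 80; reviews every 20 patients or every 4 months (40 per year ÷ 3 ≈ 13 patients).

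Assumptions: one yes/no SIR outcome per patient; historic rate 50%, the lower end of the range that Background/Significance gives for rituximab and alemtuzumab; true rate 25, 30 or 35%; stop at n = 20, 40 or 60 if x/n ≤ 0.50/2 = 0.25. After a stop, k patients already enrolled are added, up to 80 in all. Bias = Σ P(final x, final n) · x/n − p, by exact binomial recursion.

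| Looks | Overrun k | Bias in points at true 25 / 30 / 35% | Mean N |
|---|---|---|---|
| 20/40/60/80 | 0 | -3.0 / -3.3 / -2.7 | 38 / 52 / 64 |
| 20/40/60/80 | 10 | -1.6 / -1.8 / -1.5 | 46 / 57 / 67 |
| 20/40/60/80 | 20 | -1.0 / -1.1 / -0.9 | 53 / 62 / 70 |
| 40/60/80 | 20 | -0.5 / -0.4 / -0.2 | 68 / 74 / 78 |
| every 4 months | 0 | -4.3 / -4.7 / -4.1 | 33 / 46 / 59 |
| every 4 months | 20 | -1.2 / -1.3 / -1.2 | 48 / 57 / 66 |

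With historic 80% and true 40/48/56%, looks every 20 patients give -3.4/-3.3/-1.7 with k = 0 and -1.1/-1.1/-0.6 with k = 20.

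Zero overrun is the least realistic row. Reviews are triggered by enrolment or the calendar, while each patient is followed for up to six infusions or bag changes, so patients would be in progress at any stop.

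Strict trigger (exact 95% upper limit ≤ 25%; looks every 20, k = 0): bias -0.5/-0.2/-0.1 and mean N 78 or more.

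**4. Comparison with sampling error.** SE at n = 80 is √(p(1−p)/80):
- p = 0.25: √(0.1875/80) = 4.8 points
- p = 0.35: √(0.2275/80) = 5.3 points

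**5. Precision and coverage.** Exact 95% intervals are 8.7-49.1% for 5/20, 12.7-41.2% for 10/40 and 16.0-35.9% for 20/80. A stop at 20 doubles the width: (49.1 − 8.7)/(35.9 − 16.0) = 40.4/19.9 = 2.0. At looks every 20 patients, coverage of the exact interval is 94.8-97.5% under the halving rule with k = 0 to 20. Over the wider set of triggers and historic rates tried, it is about 93-98%.

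**The case for a change.** The strongest case for changing the text has three parts. First, in a list of reasons to stop, an item that only means the study has finished is redundant, so a reader may look for another meaning. Second, the monitor can recommend termination and would probably see the SIR rate. Third, the averages hide what stopped trials would report. At a true rate of 35% with looks every 20 patients, trials that reach the halving at a look report a mean of 21.8% with no overrun and 28.1% with 20 added. The final data show a halving in 28.9% of trials (no overrun) or 10.7% (overrun 20), against 3.7% at a single analysis of 80. Clarifying would cost a line.

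What stands: the phrase is undefined, the text does not expressly exclude a success stop, and the arithmetic is right.

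What does not stand is the step from there to a defect. Redundant items are common in generic stopping lists. The conditional figures describe a rule that the plan does not contain, set against a historic rate that it does not fix. No decision in the plan depends on an observed halving, so 28.9% against 3.7% is not inflation of any planned error rate. A short trial would show its imprecision in the interval already planned.

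**Conclusion.** The concern does not call for a change. The wording is loose, but the plan followed as written most naturally runs to the end of planned enrolment and follow-up and gives a sound estimate. The gap is one that a sensible team fills correctly.

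If the phrase were nevertheless used as a success rule, the average bias would be downward and modest. At reviews every 20 patients it is about 0 to 3.5 points across the triggers tried, and 0.9 to 1.8 points under the halving rule with 10 to 20 patients added after the stop. The largest value found, 4.7 points, needs reviews every 4 months and no overrun at all. These figures rest on an invented trigger, an assumed historic rate and one binary outcome per patient. Interval coverage stays near nominal, and the plan states no precision target or test against history that would be missed. For a pilot study with a descriptive primary endpoint, that is too conditional and too small to require a change to the protocol.

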### **Confidentiality and Privacy:**

Currently all data for patients who will be starting a treatment regimen that includes monoclonal antibodies either alone or in combination with chemotherapy are kept confidential. Study information for retrospective study will be obtain from EPIC EMR. All information obtained will be confidential and only need to know information will be obtain from EPIC for study purposes only. Both retrospective and prospective information will be stored on password protected, secured online REDCAP database.

### **Data Security:**

All study related charts will be scanned into EPIC and hard copy including consent form will be kept securely in the CCI research department in a locked room per CCI research department guidelines.

Study data will be entered into REDCAP database, which is password protected and HIPAA compliant. De-identified password protected data will be downloaded from REDCAP for analysis by research staff. Downloaded data will be stored on password protected CMC/UCSF encrypted computer by PI until at least 1yr post publication after which it will be destroyed per CMC/UCSF protocol. Damages from inadvertent identification of patients and protected patients information will be limited to less than minimum risk by study team.

### **Adverse Reaction and Adverse Event Reporting:**

Throughout the course of the study, all efforts will be made to remain alert to possible adverse experiences or unanticipated findings. If adverse experiences occur, the first concern will be the safety and welfare of the patient, and appropriate medical intervention will be made. Any adverse reactions to the study medication observed by the Investigator or reported by the patient, regardless of severity, will be recorded in the patient's case file and reported to the IRB.

Any patients who are discontinued from the study due to adverse experiences will be followed until their medical outcome is determined, and written reports will be provided to the IRB by the Investigator.

## **Funding Section:**

This study is paid for by a pilot research grant from the Central California Faculty Medical Group (CCFMG). The study doctors and the study staff do not have any financial or non-financial conflicts of interest regarding this study. See Appendix 3 for study budget breakdown.

